
Second, there is a direct benefit related to the potential for reactivity to behavioral survey assessments, including the surveys utilized in this research study. Reactivity is the possibility that the research methods themselves affect the behavior under study. The process of completing substance use assessments is often illuminating for participants such that they react by reducing their risk behavior. Reactivity to alcohol assessment occurs when completing alcohol surveys is associated with changes in alcohol use, specifically reduced alcohol use. Research has shown that there is reactivity to alcohol assessment for longitudinal surveys (McCambridge & Kypri; 2011; Walters et al. 2009) such that participants reduce alcohol use over time as a result of repeated assessments. Further, research indicates that completing assessments about a range of health behaviors can lead to increases in health-promoting behaviors (Miles et al., 2020; Wood et al., 2016). Thus, both parent and teen participants in Project PRISM have the potential to directly benefit from completing longitudinal behavioral assessment surveys (screening, baseline, 1-month, and 6-month surveys).

In addition, all participants may directly benefit through the provision of resources on a variety of topics including alcohol use, substance use, mental health, etc. In addition, we have a plan for identifying and referring individuals who report significantly worsening alcohol use trajectories as well as consumption of potentially lethal doses of alcohol as reported on their survey assessments. This screening process is also a potential direct benefit for participants as they have the opportunity to learn more about their drinking and potentially be referred to services, if needed. **All participants (parents and teens), at the end of participation, will be provided with referral resources available both locally and nationally, which is a direct benefit of participating in the proposed study.**

We believe that the potential risks of the study (please see below) are reasonable in relation to the importance of the knowledge gained and potential direct study benefits, which justifies the risk regarding uncomfortable survey items and risk of confidentiality. First, as noted above the direct benefit of potentially improving parent-teen communication and alcohol use outcomes outweighs potential risks related to sensitivity of questions and potential loss of privacy. Further, given that parents in the control condition will be sent the intervention website link at the end of study completion for them and their teen, all participants have potential to directly benefit from participation in this study. In addition, the potential for reactivity from Project PRISM alcohol assessments (i.e., potential for participants to reduce alcohol use as part of the research study) is a potential direct benefit. We feel the above benefits justify the risks of Project PRISM; specifically, potential benefits from reactivity leading to reduced alcohol use and benefits for parental communication justifies participants' possible discomfort with questions and confidentiality (discussed below). All participants (parents and teens) will be provided with referral resources both locally and nationally, which is a direct benefit of participating in Project PRISM. In sum, there are a multitude of direct benefits available to all Project PRISM participants.

- 3) Describe how the anticipated benefit of this research is at least as favorable to the subjects as that to be received by available alternative approaches for the subjects.

If the participant chooses not to participate in the study but has questions about alcohol or other substances, we can provide them with a list of information and referrals within the community. See Resource Information Email (Appendix C).

- 4) Describe any potential RISKS OR DISCOMFORTS in detail. Use evidence from clinical and/or animal studies to evaluate the level of potential hazards associated with participation in the research protocol. Indicate the methods for detecting adverse reactions. Describe the procedures for protecting against or minimizing potential risks (e.g., confidentiality, reputational injury, direct injury or harm to subject, etc.) and assess their effectiveness. Discuss why the risks to the subjects are reasonable in relation to proposed benefits to mankind. Be sure to describe any anticipated adverse events that might occur during the course of the study.

The study procedures involve potential risk to participants. The consent procedures will make clear all of the potential risks of study participation. The most significant risk to participants in this research is loss of privacy and unauthorized release of confidential information. This could occur if data on an individual participant, or the information that he or she was participating in a study of alcohol behavior, were to be released to anyone outside the study. Psychological risks posed by the research are primarily related to the sensitivity of some of the survey items. Items include thoughts, feelings, and personal difficulties that may be private and personal behavior such as alcohol use and related

negative consequences. These questions may make participants uncomfortable, or be perceived as an intrusion on their privacy. In addition, participants are asked to report on potentially illegal behaviors such as drinking under the legal drinking age or using marijuana in the state of Texas. Answers to these questions could pose a risk if the information were known and linked to identifiable individuals. We were automatically issued a Certificate of Confidentiality from NIAAA to prevent disclosure of sensitive or illegal behaviors. We have been using similar procedures on multiple NIH-funded studies with no adverse events or loss of confidentiality on any project. We have taken steps to protect participants against potential risks posed by their participation in this research. Participants will be fully informed of the range of items and the most sensitive and personal topics in the consent form, and will be informed that they are free not to answer any question they wish not to answer, and can refuse to participate or withdraw from participation at any time without penalty. Psychological risks of experienced invasion of privacy or increased awareness or concern about one's behavior as a result of completing the surveys and potential loss of confidentiality will be addressed as a risk in the consent documents. Participants are encouraged to contact the investigators at any time to discuss any concerns they might have. Participants who express interest in seeking help for substance-related problems or for psychological distress will be offered referral information and will be emailed a copy of the Resource List (see Resource List Email). Participants will not be restricted from seeking other alcohol, substance use, or mental health education, prevention, or treatment opportunities, and we will assess for use of other services at each assessment.

We do not ask any survey items that assess suicide, child abuse, or child neglect, so we would have no data related to these topics to report. However, if a participant discloses this information we will report it to the appropriate official/agency according to Texas State Law.

We have taken steps to protect participants against potential risks posed by their participation in this research. Participants will be fully informed of the range of items and the most sensitive and personal items in the consent forms including alcohol and marijuana use, and will be informed that they are free not to answer any question they wish not to answer, and can refuse to participate or withdraw from participation at any time without penalty. Psychological risks of experienced invasion of privacy or increased awareness or concern about one's behavior as a result of completing the surveys and potential loss of confidentiality will be addressed as a risk in the consent documents. In order to protect against risks posed by a potential loss of confidentiality, we will take the following steps: First, all data will be identified only by a unique identifier, which will be randomly generated for study purposes. These unique identifiers will be embedded in individual survey links such that they do not need to be entered by participants or known by participants. Identifiable information entered online (such as contact information) will be downloaded and stored separately from participants' responses, but will be identified by the unique identifier. A master list of names and unique identifiers will be stored in a password-protected database, on a password-protected computer with restricted access, and will be available only to senior research staff and the PI on this project. All members of the research team have received or will receive training that includes emphasis upon the importance of confidentiality of information, and all personnel on the project (including research assistants and study staff) will complete the required NIH training in protection of human research participants. All staff will sign confidentiality statements. Third, to maintain confidentiality of data submitted over the internet, participants will be required to log into a secure and HIPAA compliant servers using their unique identifier created for study purposes. The PI has extensive experience with conducting online recruitment and assessment with no adverse events ever occurring from this method of data collection or stated procedures. Fourth, NIH issues a federal Certificate of Confidentiality through the Department of Health and Human Services. This certificate

offers the highest protection available by law for research data. We previously used these certificates in our work with drinkers, marijuana users, high school students, college student gamblers, and those who engage in risky sexual behavior. Participants will be informed of these risks and protections in the informed consent process. All recruitment contacts will emphasize the voluntary nature of participation, to reduce risks of experienced coercion. Finally, participants will be notified of the potential risk that the information provided may not be helpful, and will be provided with information about where else they might seek information about alcohol use, marijuana use, or receive substance use-related services if desired.

A plan is in place for identifying and referring individuals who report significantly worsening alcohol use trajectories as well as consumption of potentially lethal doses of alcohol (BAC's above .35) and potential for alcohol use disorder as measured on the AUDIT. Specifically, the baseline, 1-month, and 6-month surveys will be screened immediately upon submission for indication of significant risk based on criteria established in our prior trials of this nature and the research literature (i.e., a score of 8 or more (age 18-25)/a score of 4 or more (age 15-17) on the AUDIT on baseline, 1-month, or 6-month surveys in combination with a BAC in the past month exceeding .35%; Chung et al., 2000; 2002). The AUDIT total score is used to assess the risk of alcohol use disorder. A score of 8 or more is suggested for identifying hazardous drinking behaviors among adults, and a score of 4 or more is suggested for identifying hazardous drinking behaviors among adolescents as young as 13. Thus, both outcomes (8+AUDIT and 4+AUDIT, respectively) will be used to assess hazardous alcohol use for referral in combination of .35% BAC. Participants who meet this criterion will be emailed local referral information. All such contact will be noted in the tracking database. In our ongoing trials, we have used this procedure without incident. Information regarding the potential for a follow-up contact by the investigators to clarify responses or provide information is included in the consent documents. Participants are also informed in the Informed Consent that they are free to seek other services for their alcohol use. This structure is currently in place and approved at both the local and federal level on all our existing drinking and health-risk behavior studies. **All participants (parents and teens), at the end of participation, will be provided with referral resources available both locally and nationally.**

If an adolescent in the study reports significantly worsening alcohol use trajectories or consuming potentially lethal doses alcohol, their parents will not be informed about this report due to confidentiality.

See Referral Information Email in Appendices.

Participants are encouraged to contact the investigators at any time to discuss any concerns they might have. Participants who express interest in seeking help for substance-related problems or for psychological distress will be offered referral information. Participants will not be restricted from seeking other alcohol, substance use (i.e., marijuana) or mental health education, prevention, or treatment opportunities.

H. Payment/Compensation - Describe any financial payments for subject participation (e.g. compensation for time and travel). Indicate any partial payment schedule for less than complete study participation. Recall that payments cannot be perceived as coercive (overpayment for time and effort). Remember: payments are NOT benefits.

Compensation. Each participant will be mailed a Greenphire Mastercard that will be loaded with \$25 for completion of the baseline survey. See Appendix C what a Greenphire Mastercard looks like. Participants will also be provided Greenphire Mastercard FAQs and information on how the Greenphire Mastercard can be used via mail after completion of the baseline survey. Participants are notified in the baseline survey end page and in the frequently asked question sheet that they will need to contact us via email or phone when they receive their card. At this point, we will load the money onto their Mastercard. If a participant does not call/email confirming they have received their Greenphire Mastercard within 1-2 weeks after their card was mailed, we will periodically contact them via phone, text, and email to confirm if they have received their card. In the event they have not received it after a prolonged period of time, we will re-send them another Greenphire Mastercard to their preferred address.

Each Greenphire Mastercard has a unique identifier. In monthly Greenphire reports, this identifier will indicate payment amount and payment date for each payment to participants. This monthly Greenphire report will verify payment for compliance purposes. Greenphire has an option to request or not request social security numbers for payment. We do not request this information as it is not a requirement for Greenphire or for study purposes.

We will advise individuals without a government-issued ID that they will not be able to use their Greenphire Mastercard to get a cash advance at a bank.

Compensation Schedule:

Online screening survey: 5-10 minutes, no incentive

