Parent/teen dyads who meet inclusion criteria and pass phone verification will be emailed and texted a baseline survey link. The baseline survey will include questions about demographics, social media literacy, parenting, drinking and drug use, drinking cognitions, mental health, and other health behaviors and will take approximately 45 minutes to complete. Questions in the assessments will also include topics about sexual orientation, gender identity, religion, and relationship status. For those in the Intervention group, items in the 1-month follow-up survey will assess satisfaction with the intervention website. If we do not receive the completed assessment at each follow-up (Baseline Assessment, 1-month, and 6-month assessment), we will periodically send reminders – via email (up to 8), text (up to 8) and/or phone/voicemail (up to 5). Parents and teens can earn \$25 for baseline, \$35 for the 1-month follow-up, \$40 for the 6-month follow-up, meaning that all participants can earn up to \$100.

Baseline Assessment, 1-Month, and 6-Month Measures.

While the baseline, 1-month, and 6-month surveys will contain overlapping content, we may decide to include or exclude a measure over the course of the study, with IRB approval via a modification. Thus we are electing to not indicate in the consent form that the three surveys will be the same. Overlap in surveys is indicated by the overall content areas of surveys that are provided in the consent form. Behavior will be reported over lifetime

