(baseline) and the past month to reduce problems with retrospective recall and overlap. Demographics will include age, height, weight, and family history characteristics. Parent-teen relationships will be evaluated in terms of parent-teen communication regarding both alcohol and social media ($\alpha = .53\text{-.75}$; Turrisi et al., 2000), and parent-teen relationship closeness ($\alpha = .90$; Buchanan et al., 1991). To determine the nature of parental involvement and monitoring of teens, parental monitoring will be assessed with the Parental Monitoring and Knowledge Scale ($\alpha = .81$; Branstetter & Furman, 2013) and the Parental Monitoring of SNS measures ($\alpha = .67\text{-.88}$; Livingstone & Helsper, 2008). In order to evaluate parental attitudes towards teen drinking, parents will complete the Parental Approval of Drinking Scale ($\alpha = .85$; Wood et al., 2004). Teens' perception of parental attitudes toward drinking will be assessed with the Perceived Parent Approval of Drinking Scale ($\alpha = .85$; Wood et al., 2004). Both parent and teens will be asked about their own social media use with the Social Media Scale, parents will also report perceptions of their teen's social media use with the same scale. Social media literacy will be determined with the Alcohol Specific Media Literacy Scale and the Alcohol Specific Social Media Literacy Scale (Martino et al., 2016; Unger et al., 2003).

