Parents and teens will be asked questions regarding their alcohol and substance use. Family history of alcohol (baseline only) as well as lifetime and past year alcohol use (teen only) will be assessed (Johnston et al., 2014; Miller & Marlatt, 1984). Marijuana Use (Johnston et al., 2012) will be measured with items including lifetime and past year marijuana use for teens, and past month marijuana use for both parents and teens. Teens will also be asked about their perceived access to marijuana (Harpin et al., 2018). Other substance use, including co-use cognitions and behaviors, will be assessed for lifetime and past month frequency using the Customary Drinking and Drug Use Record (baseline only; $\alpha = .70\text{-.94}$; Brown et al., 1998; Schafer & Brown, 1991) as well as an adapted version that assesses co-use of substances. Drinking will be assessed with the Daily Drinking Questionnaire and the Quantity Frequency Index (DDQ; $\alpha = .73$; Collins et al., 1985; Dimeff et al., 1999; [name] & Neighbors, 2004), and the Alcohol Use Disorders Identification Test ($\alpha = .85$; Babor et al., 2001, Daepen et al., 2000).

Teens will be asked about additional behaviors, cognitions, and perceptions related to their substance use. Consequences will be assessed with the Young Adult Alcohol Consequences Questionnaire ($\alpha = .79$; Read et al., 2006, 2007). Descriptive norms will be assessed by asking the perceived frequency and quantity of drinking and marijuana ($\alpha = .80$; Baer et al., 1991; [name] & Neighbors, 2004; Neighbors et al., 2008) among typical men/women their age as well as close friends. Attitudes items will ask how much the participant approves or disapproves of a series of alcohol behaviors ($\alpha = .85$; Ajzen, 2006; Todd & Mullan, 2011). Injunctive norms will be measured using a series of statements that assess participants' perceptions of other's attitudes and close

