friends' attitudes towards toward drinking and marijuana use ($\alpha = .70\text{-.93}$; [name] et al., 2010; LaBrie et al., 2010). Perceived vulnerability will be assessed by asking participants how likely they think it is that certain alcohol consequences will happen to them ($\alpha = .82$; Gerrard et al., 2008; [name] & Stock, 2011). Prototypes will be measured by items that assess how favorable participants feel toward the typical drinker of the same sex and age ($\alpha = .87$; Gerrard et al., 2002, 2006). Experience of alcohol use will consist of one indicator of several key variables (i.e., age at first drink, quantity, frequency, perceived close friend alcohol use, and perceived access to alcohol). The willingness measure will assess willingness to use alcohol in certain scenarios ($\alpha = .85$; Gerrard et al., 2002, 2008). Intentions for alcohol use will be assessed by items on intended frequency and quantity ($\alpha = .83$; Ajzen, 2006; Gerrard et al., 2006). Perceived access to substance use will be assessed with a modified version of The Perceived Access to Alcohol and Other Drug Scale ($\alpha = .86$; Kuntsche et al., 2008). Anxiety and depression will be measured using the PROMIS Anxiety v1.0 and PROMIS Pediatric Anxiety v1.1 Short Form ($\alpha = .96$; Cella et al., 2010) and the PROMIS Depression and PROMIS Pediatric Depression v1.1 Short Form instruments ($\alpha = .96$; Cella et al., 2010), respectively.

Lastly, both parents and teens in the intervention group will be asked to complete a 1 month satisfaction scale related to their experience, perceptions, and interactions with the intervention website.

1. Data Analysis and Data Monitoring –

In order to evaluate the pilot study in Phase 2 (Aim 2), we will examine (a) recruitment and retention rates,(b) parent post-intervention feedback as measured at 1 month follow-up (i.e., accessible, usable, convenient, relevant, and helpful),(c) teens' rates of alcohol initiation and use, alcohol-related negative consequences, attitudes toward posting about alcohol on SNS, perceived vulnerability to the risks of posting alcohol displays on SNS, and normative perceptions about how many teens post alcohol displays on SNS, d) parental knowledge and attitudes toward alcohol and SNS, and e) parent and teen report of alcohol and SNS related communication which will provide base rates and variance in outcomes to determine adequate power for a future clinical trial R01 application.

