This pilot will *explore treatment differences and determine preliminary effect sizes* for teens' drinking and risky cognitions as well as parents' knowledge about alcohol and SNS, and parent- and teen-reported outcomes will be analyzed in separate models. All models will have *three* repeated measures (i.e., baseline, 1 month, and 6 month follow-up), yielding up to 450 Level 1 observations (repeated-measures) across 150 Level 2 cases (teens or parents). Prior to inferential statistics, univariate and bivariate descriptive statistics will be used to assess distributions and simple associations among variables. Primary teen-reported outcomes are alcohol use and negative consequences (both count outcomes) as well as cognitions (attitudes, norms, and perceived vulnerability related to SNS alcohol displays; all modeled as normally distributed outcomes). Primary parent-reported outcomes will be knowledge about alcohol and SNS (modeled as normally distributed outcomes). Given the repeated measures design, generalized linear mixed models (GLMM; Raudenbush & Bryk, 2002) will be used. GLMM (aka hierarchical generalized linear models) allow for non-normal outcomes and missing data.

2. Data Storage and Confidentiality –

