completion, thus all participants may directly benefit from participation in this study not just those originally randomized to intervention. First, because this is an intervention specifically designed to improve parental communication and reduce risky social media use and drinking among adolescents and young adults, enrollment in the study over a course of 6 months is likely to have a direct benefit on both parents and teens as it may increase parent-teen communication and reduce adolescent and young adult alcohol as a result of completing Project PRISM. Any study that involves an intervention could have an anticipated direct benefit as participants will receive an intervention that they would not otherwise receive. Research indicates that parent-based interventions, such as the one proposed herein, have proven successful at reducing the odds that nondrinking teens and young adults will initiate alcohol use (Ichiyama et al., 2009) and on general alcohol consumption (e.g., Doumas et al., 2013; Ichiyama et al., 2009; Turrisi et al., 2001, 2010, 2013). A systematic review (Kuntsche & Kuntsche, 2016) supported the idea of using parents in prevention programs. Across studies and concepts, they found evidence that participating in parent-based interventions *improved* parenting measures such as rule-setting, monitoring and parent-child communication as well as the *prevention and reduction of adolescent substance use*. Thus, both parents and teens may directly benefit from participation in a parent-based intervention such as Project PRISM. Second, much of the intervention content related to parent-teen communication and engaging in non-reactive and non-judgmental conversations with their teens is in line with mindful parenting, which can be defined as the ongoing process of intentionally bringing moment-to-moment, non-judgmental awareness and communication to parenting (Duncan et al., 2009). This non-judgmental moment-to-moment communication can support parents in becoming more aware of what and how they communicate and allows parents to pause and reflect before communication and consider current communication and relationships in context of the long-term relationship that they have with their teen, as well as attend to their teen's needs. Research indicates that parents who either have a natural capacity for, or learn practices of mindful parenting will be more likely to develop higher quality relationships with their children (Duncan et al., 2009) and that teens whose parents follow practices of mindful parenting including non-judgmental communication and listening with full attention and openness are less likely to experience conflict with their parents and thus are more likely to self-disclose when they have concerns (Smetana et al., 2006). Given that many of the recommendations in the proposed intervention focus on mindful parenting (e.g., non-judgmental and non-reactive communication, relationship building, honesty and openness, listening with full attention, compassion for self and child), participation in this study may have direct benefit on the quality of communication and relationships between parent and teens.

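### Does the plan need to define alcohol initiation and commit to a 6-month item that marks it?

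*Combined protocol and SAP*

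**What the plan says.** The Data Analysis and Data Monitoring part of Section E names "teens' rates of alcohol initiation and use, alcohol-related negative consequences" among the things the pilot will examine, and says the listed outcomes are to inform the power of a later trial. The same part then sets out what is modelled: "Primary teen-reported outcomes are alcohol use and negative consequences (both count outcomes"), together with cognitions about alcohol displays on social media. Initiation is not in that list, nor among the teen hypotheses under Aim 2 in Section A. Section G cites earlier parent-based programmes as "reducing the odds that nondrinking teens and young adults will initiate alcohol use". That describes other research, not this trial's risk set.

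On measurement, the text under the heading for the baseline, 1-month and 6-month measures gives a general rule: "Behavior will be reported over lifetime" and, after an opening bracket, "baseline) and the past month to reduce problems with retrospective recall and overlap". Further on under the same heading, "lifetime and past year alcohol use (teen only) will be assessed", and the experience-of-use measure covers "age at first drink, quantity, frequency, perceived close friend alcohol use, and perceived access to alcohol". No survey is named for these items. The heading also carries a general reservation that "we may decide to include or exclude a measure over the course of the study", subject to IRB approval of a modification. The questionnaires are separate attachments.

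**The concern.** A rate needs an event and a denominator, and the protocol states neither for initiation. The teen eligibility criteria in Section F set no condition on drinking history, so drinkers and never-drinkers can both enrol. Randomization is balanced on alcohol use, but the levels of that factor are not given.

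Item timing is also unsettled. The general rule ties the lifetime window to baseline, which could mean that follow-up surveys ask only about the past month. A teen who first drank in the third month and not in the sixth would then be missed. An item left out of the 6-month survey cannot be recovered afterwards. Since these rates are meant to help plan the next trial, a figure with an unstated denominator or incomplete capture could mislead that planning.

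**Working it through.** **The plan's own figure.** 75 + 75 = 150 teens, and 150 × 3 surveys = 450 observations, as stated. That figure belongs to the repeated-measures models. The protocol gives no expected rate, power or precision for initiation, so the rest is illustration under stated assumptions.

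**Can initiation be computed from what is planned?** Take the at-risk set as teens with no lifetime use at baseline, and the event as any alcohol use reported at 1 or 6 months. The first needs a lifetime report at baseline; the second needs at least a past-month report at follow-up. The general rule supplies both, so a usable rate exists without any further item.

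**Denominator.** Let s be the share of never-drinkers at baseline (assumed), with 20% of them initiating (assumed). At risk = 150 × s; initiators = 0.20 × 150 × s; share of all teens = initiators / 150.

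| s | At risk | Initiators | Of never-drinkers | Of all 150 |
|---|---|---|---|---|
| 30% | 45 | 9 | 20% | 6% |
| 50% | 75 | 15 | 20% | 10% |
| 70% | 105 | 21 | 20% | 14% |

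The two rates differ by 1/s, that is 3.3, 2.0 and 1.4 times. This is only the inverse of an assumed share. Once the number at risk is reported, either rate can be obtained from the other.

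**Look-back, if follow-up used past-month items only.** Surveys at 1 and 6 months cover the first and sixth months, 2/6 = 33% of follow-up. Calendar coverage is not detection, because a teen who starts in the four uncovered months is still found if he or she also drinks in the sixth. With onset uniform over six months (assumed) and q the probability of that, detection = (2 + 4q)/6:

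- q = 0: 2/6 = 33%
- q = 0.5: 4/6 = 67%
- q = 1: 6/6 = 100%

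A single lifetime, past-year or age-at-first-drink item at 6 months covers all six months.

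**Precision, for scale.** Splitting the at-risk sets in two and rounding down gives 22, 37 and 52 teens per arm. At about 20% initiating, that is 4, 7 and 10 events, with Wilson 95% intervals of 7.3–38.5%, 9.5–34.2% and 10.8–31.9%. Power to separate 20% from 10% (two-sided 5%, assumed) is 15%, 22% and 30%. At q = 0.5 a true 20% would read as 0.20 × 4/6 = 13.3%, inside all three intervals. At the extreme q = 0 it would read as 0.20 × 2/6 = 6.7%, just below all three.

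**Which reading of item timing does the text favour?** The heading covers all three surveys. Where a measure is restricted to baseline, the alcohol and substance use text says so: it does for family history and for the customary drinking and drug use record. Lifetime and past-year alcohol use stands in the same sentence as the first of those marks and is labelled for teens only, with no limit to baseline. The general rule cannot be a complete list of windows, because it omits the past-year window that appears later. The text therefore leans towards the items being repeated, without saying so outright.

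**The case for a change.** The strongest case for a change is that wording costs almost nothing, the rates are wanted for the next trial, and a 6-month item not asked is lost for good. Part of that stands. The definition is unwritten, and the general rule on windows does not sit neatly with the later item list. If the follow-up surveys did use the past month alone, teens who started in the gap and did not drink in the sixth month would be missed.

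The rest carries less weight. Whether the 6-month survey holds an onset item is a fact about the attached questionnaires, and a synopsis written for an IRB need not list items survey by survey. The reservation about dropping measures applies to every measure and needs IRB approval, so it is no sign that this item is at particular risk. Dividing by all 150 teens is a reading the protocol nowhere adopts; initiation ordinarily means first use, and Section G pairs the word with nondrinkers. Descriptive statistics are already planned ahead of the models, which is where a count at risk and a count initiating would appear.

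**Conclusion.** No change is needed. This is missing detail on a secondary descriptive quantity, of a kind analysts fill sensibly: first reported use among teens with no lifetime use at baseline, with the number at risk shown. It cannot alter the planned comparisons of drinking, consequences, cognitions or parental knowledge.

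The worst consequence is under-capture if follow-up asked about the past month alone. Detection would then lie between 33% and 100% of initiators, given uniform onset, and the text points away from that case. Even with full capture, per-arm intervals would run from about 7–39% to 11–32% for never-drinker shares of 30% to 70% and a 20% rate, so a pilot of this size gives only a rough base rate. The shares, the 20% rate and q are assumptions, and dropout is ignored. The survey instruments, which would settle the timing, are not part of the text reviewed.
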